9.0 Criteria for Response

Response to CNB will be assessed by differences in post-operative pain score, number of analgesic medications taken and time to discharge.

10.0 Criteria for Removal from the Study

Any patient requesting withdrawal from the study will be removed. Otherwise, study participation will terminate after the three day follow-up telephone conversation has been completed.

11.0 Statistical Consideration/Number of Patients

11.1 Objectives

This is a trial to determine whether the use of a caudal nerve block (CNB) and general anesthesia in patients undergoing surgery for penile prosthesis results in decreased post-operative pain compared with patients having only general anesthesia. Patients will be randomized with a 1:1 ratio to receive either CNB or general anesthesia. The primary endpoint is the post-operative pain medication usage during PACU stay. The secondary endpoint is the proportion of patients with no pain immediately after surgery.

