1.2 Secondary Objectives

- 1.2.1 To determine whether the use of a CNB in patients undergoing penile prosthesis surgery results in decreased immediate postoperative pain in the first 24 hours after surgery compared with patients having only general anesthesia as determined by postop pain score.
- 1.2.2 To determine whether the use of a CNB in patients undergoing penile prosthesis surgery results in a decreased length of hospital stay compared with patients having only general anesthesia.

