5.3 Postoperative

5.3.1 Pain will be assessed using the numeric rating scale (NRS). The NRS is scored by numeric integers, 0 through 10. The NRS will be used verbally.

- 5.3.2 When using the NRS for pain, the provider will ask, "On a scale of zero to ten, where zero means no pain and ten equals the worst possible pain, what is your current pain level?"
- 5.3.3 Pain will be treated and documented in the PACU dependent on the patient's pain score:
 - Pain score 0-2 receive no treatment
 - Pain score 3-5 receive fentanyl 25mcg iv then reassess pain score in 15 minutes +5min.
 - Pain score 6-8 receive fentanyl 50mcg iv then reassess pain score in 15 minutes +5min.
 - Pain score 9-10 receive fentanyl 75mcg iv then reassess pain score in 15 minutes +5min.
- 5.3.4 If 250 mcg Fentanyl is exceeded, then change to use of Dilaudid 0.5mg IV to a maximum dose of 10mg total.
- 5.3.5 Patients in both groups will be discharged using the same standard PACU discharge criteria. Specifically, patients will be discharged from the PACU when they meet PACU discharge criteria.
- 5.3.6 Pain will be evaluated 15 minutes after arrival to PACU and every 15 minutes thereafter until discharge from PACU. If the patient has been discharged on the day of surgery, the follow-up will be performed by telephone call directly to the patient. Time to discharge, frequency of pain medications and pain medication totals will be recorded.

- 5.3.7 Pain will be evaluated using the NRS with scores of 0-10, where 0 is no pain and 10 is the worst pain. Pain will also be evaluated by the amount of IV and oral pain medicine administered in the first 24 hours post-operatively.
- 5.3.8 Equianalgesic values of IV morphine in mg will be tallied based on each patient's total pain medication administration.
- 5.3.9 An additional follow-up telephone call will occur 3 days after surgery to evaluate pain and amount of pain medications taken.

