11.2 Sample Size and Power

This is a randomized, blinded trial designed to evaluate the efficacy of the caudal nerve block (CNB) in combination with the general anesthesia (GA) comparing to the GA-only on patients undergoing penile prosthesis surgery. The primary objective is to determine if the CNB + GA can result in decreased post-operative pain medication usage during PACU stay comparing to the GA-only. One hundred four patients will be randomized with a 1:1 ratio to each of the treatment arms. In a retrospective trial. PA15-0080, the mean ± SD for the post-operative pain medication usage was 21.6 \pm 13.6 mg for the GA-only group (n=59) and 13.9 \pm 11.0 for the CNB + GA group (n=26). With a sample size of 104 patients (52 for each treatment arm), the study will have at least 81% power to detect the difference in post-operative pain medication usage between 21.6 for the GA-only arm and 13.9 for the CNB + GA arm assuming a common standard deviation of 13.6 as observed in the retrospective study. A twosided Type I error rate of 0.05 was used (EAST 6.3.1, Cytel Inc 2015). One interim analysis will be performed to allow for the early termination of the trial in light of evidence that the CNB + GA treatment is superior to the GA-only treatment or there is no difference between the two treatment arms. In order to provide an overall significance level of 0.05 for the study, the interim analysis will use an O'Brien-Fleming stopping rule. The interim analysis will be performed when 52 out of the 104 patients have been observed. Using O'Brien-Fleming test boundaries, we will reject the null hypothesis at the interim and final analyses when the absolute value of the Z-score is larger than or equal to 2.963 and 1.969 (the corresponding p-values are ≤ 0.003 and 0.049), respectively. We will reject the alternative hypothesis at the interim and final analyses when the absolute value of the Z-score is less than or equal to 0.338 and 1.969 (the corresponding p-values are ≥ 0.736 and 0.049), respectively. The secondary objective is to compare the post-operative pain in the first 24

hours after surgery between the two treatment arms. The patients will be blinded for the treatment assignment to avoid potential biases.

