11.3 Analysis Plans

Patients' demographic information at baseline will be collected. We will use mean, standard deviation, median, and range to summarize continuous variables such as blood pressure, heart rate, temperature, pain medication usage, pain and nausea scores, and frequency counts and percentages for categorical variables such as adverse events. We will use the student t-test or the Wilcoxon rank sum test to compare continuous variables between two patient groups. The Fisher's exact test or Chi-square test will be applied to assess the association between two categorical variables. Linear regression will be utilized to assess the effects of patient prognostic factors on the post-operative pain medication usage and the pain score in the first 24 hours.

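### The 24-hour pain objective has no defined score, and the plan requires no timed NRS score after PACU discharge that could supply one

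*Combined protocol and SAP*

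**What the plan says.** Section 1.2 sets two secondary objectives. The first (1.2.1) asks whether the block gives "decreased immediate postoperative pain in the first 24 hours after surgery compared with patients having only general anesthesia as determined by postop pain score". The second (1.2.2) asks whether it "results in a decreased length of hospital stay compared with patients having only general anesthesia".

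Section 11 treats the pain objective in three ways:
- 11.1: "The secondary endpoint is the proportion of patients with no pain immediately after surgery".
- 11.2: "The secondary objective is to compare the post-operative pain in the first 24" hours, between arms.
- 11.3: linear regression for effects of prognostic factors on "the post-operative pain medication usage and the pain score in the first 24 hours", plus a t-test or Wilcoxon test for continuous variables in general.

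On measurement, 5.3.1 and 5.3.7 name the NRS as the postoperative pain scale, and the scripted question in 5.3.2 asks "what is your current pain level". Scores are taken straight after surgery (5.3.10) and then at quarter-hour intervals until the patient leaves PACU (5.3.6). Under 5.3.3, "Pain will be treated and documented in the PACU dependent on the" patient's score, with fentanyl given by score band. The morning after surgery, in hospital or by telephone, 5.3.10 calls for the amounts of intravenous and oral analgesic. A further call three days after surgery covers pain and medication (5.3.9, 7.0).

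**The concern.** The objective concerns a 24-hour period, the named endpoint is a single early time point, and the variable in the analysis section is not defined. If sites follow the schedule exactly, no score need exist for the period between leaving PACU and 24 hours.

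Two consequences follow. First, the comparison labelled 24-hour would be a PACU comparison. The number of PACU scores per patient depends on length of PACU stay, and each score follows treatment triggered by the previous one, which can narrow a difference between arms. Such a comparison says little about whether relief lasts once the patient has left PACU, although section 2.1 gives less postoperative pain and avoiding an overnight stay as reasons for seeking other forms of anesthesia. Second, if staff do record a score next morning on their own initiative, the analyst is free to choose among first, worst, mean, time-weighted or last score after seeing the data.

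A score that was not asked for cannot be recovered on day 3, because the scripted question is about pain at that moment.

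**Working it through.** **1. The plan's own figure.** The only power statement is for PACU analgesic use (11.2): 21.6 against 13.9, SD 13.6, 52 per arm, two-sided 0.05.
- Difference: 21.6 − 13.9 = 7.7. Standard error: 13.6 × √(2/52) = 2.667. Ratio: 7.7 / 2.667 = 2.887.
- Normal approximation: Φ(2.887 − 1.960) = 82.3%. Noncentral t: 81.6%. Two-look simulation with the stated boundaries and binding futility: 81.3%.

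The stated 81% therefore reproduces, and nothing in it depends on the pain score.

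**2. What each contact requires.**

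| Contact | Source | Timed NRS score required? |
|---|---|---|
| Straight after surgery / PACU arrival | 5.3.10, 7.0 | Yes |
| Quarter-hourly in PACU | 5.3.6 | Yes |
| Telephone follow-up after same-day discharge | 5.3.6, read with 5.3.10 | Not written in |
| Morning after, in hospital or by telephone | 5.3.10 | No; medication amounts only |
| Day 3 | 5.3.9, 7.0 | Pain is named, but outside 24 hours |

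The last score with a stated time is at PACU discharge. Section 5.3.7 names the NRS again without a time, and its 24-hour item is medication.

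**3. How much the undefined summary could matter (illustration only).** Assumptions not in the documents: PACU stay L of 1 to 3 h, and one morning score taken at T = 16 to 24 h.
- Scheduled scores to the end of PACU: 4L + 1 = 5 (L = 1) to 13 (L = 3).
- Weight of one morning score in a plain mean: 1/(4L + 2) = 1/6 (16.7%) to 1/14 (7.1%).
- Weight in a trapezoidal time-weighted mean: (T − L)/(2T) = 6.5/16 (40.6%) to 11.5/24 (47.9%).
- Share of that window that is interpolated: (T − L)/T = 13/16 (81.3%) to 23/24 (95.8%).

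Suppose the arms differ by 2 points in PACU and by 0 next morning. The reported difference is then:
- PACU scores only: 2.0
- Plain mean: 2 × 5/6 = 1.67 to 2 × 13/14 = 1.86
- Time-weighted mean: 2 × (1 − 0.479) = 1.04 to 2 × (1 − 0.406) = 1.19
- Morning score alone: 0

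If the difference were a constant 2 points, all four would give 2.0. The spread reflects the assumed pattern and does not estimate what this trial would show.

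**4. Precision of a morning score.** With 52 per arm, no early stop and an assumed NRS SD of 2 to 3, the 95% CI half-width is t(0.975, 102) × SD × √(2/52) = 0.78 to 1.17 points. Power of 80% corresponds to a standardised difference of 0.555, that is 1.11 to 1.66 points. If the trial stopped at the interim with 52 patients in total, the half-width would be about √2 times larger.

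**The case against.** The strongest reply is that a morning pain score was intended and only the drafting is loose. Section 5.3.1 makes the NRS the instrument for postoperative pain generally. Section 5.3.7 sets it beside 24-hour medication use. Section 5.3.10 speaks of patients who lack relief at follow-up, and 5.3.9 calls the day-3 contact additional. For discharged patients, the telephone contact in 5.3.10 is plausibly the call mentioned in 5.3.6, so that call has a time and some content. All of this stands, so a reader should not infer that no pain enquiry after PACU was planned. It does not close the gap: a hint of an enquiry is not a recorded, timed score, and staff could comply fully without taking one.

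A reader might also infer that length of stay has been left out. The documents do not support that. Time to discharge is recorded (5.3.6), assessed with reasons for delay (7.0), used as a response criterion (9.0) and testable under 11.3. Section 5.3.5 uses the word for PACU ("patients will be discharged from the PACU when they meet PACU discharge criteria"), but 1.2.2 plainly means hospital stay. Only a wording alignment is needed.

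Likewise, patients too sedated to be scored are re-asked every quarter-hour (5.3.10), so the first obtainable score is the natural reading for the immediate endpoint.

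Finally, it is fair to say that a single next-morning score does not represent a 24-hour period. It should stand beside the PACU summary and not replace it.

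**Conclusion.** The point holds. Objective, endpoint and analysis variable do not match for 24-hour pain, and a trial run exactly as written could not compare pain scores beyond PACU. This rests on the text alone.

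The effect on the secondary result cannot be sized from the documents, which give no NRS standard deviation, PACU duration or time course of effect. The 0-to-2.0 range in the working depends on a pattern chosen to separate the summaries, and should not be read as an expected bias. Nor does the gap reach the primary comparison: PACU analgesic use, its sample size and its power are unchanged.

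The plan should be amended on this point, but the trial's main conclusion does not hang on it.

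**What to change.** - **5.3.10:** at the morning-after contact, ask every patient the 5.3.2 NRS question, at the bedside or by telephone, and record the clock time.
- **11.1 and 11.3:** before data are seen, name the pain-score endpoints for objective 1.2.1. These are the morning-after NRS, reported on its own, and one prespecified per-patient summary of the PACU scores, reported separately. Describe neither as covering the whole 24 hours, and state which one 11.3 means by its 24-hour pain score.
- **Immediate endpoint:** keep the pain-free proportion, based on the first assessable score, and report by arm how many patients could not be assessed at first. Do not add an analysis restricted to those assessable at first asking. It would condition on sedation after randomisation, which could differ by arm because 5.1.5 lists a holding-area fentanyl item for Group II only.
- **Wording:** list length of hospital stay in section 11, distinct from PACU time.

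The cost is one question per patient at a contact already planned, which for inpatients may mean a brief bedside visit, plus text edits. Sample size does not change. Overnight pain stays unmeasured and the morning score may fall short of 24 hours; the report should say both.

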11.2 Sample Size and Power

This is a randomized, blinded trial designed to evaluate the efficacy of the caudal nerve block (CNB) in combination with the general anesthesia (GA) comparing to the GA-only on patients undergoing penile prosthesis surgery. The primary objective is to determine if the CNB + GA can result in decreased post-operative pain medication usage during PACU stay comparing to the GA-only. One hundred four patients will be randomized with a 1:1 ratio to each of the treatment arms. In a retrospective trial. PA15-0080, the mean ± SD for the post-operative pain medication usage was 21.6 \pm 13.6 mg for the GA-only group (n=59) and 13.9 \pm 11.0 for the CNB + GA group (n=26). With a sample size of 104 patients (52 for each treatment arm), the study will have at least 81% power to detect the difference in post-operative pain medication usage between 21.6 for the GA-only arm and 13.9 for the CNB + GA arm assuming a common standard deviation of 13.6 as observed in the retrospective study. A twosided Type I error rate of 0.05 was used (EAST 6.3.1, Cytel Inc 2015). One interim analysis will be performed to allow for the early termination of the trial in light of evidence that the CNB + GA treatment is superior to the GA-only treatment or there is no difference between the two treatment arms. In order to provide an overall significance level of 0.05 for the study, the interim analysis will use an O'Brien-Fleming stopping rule. The interim analysis will be performed when 52 out of the 104 patients have been observed. Using O'Brien-Fleming test boundaries, we will reject the null hypothesis at the interim and final analyses when the absolute value of the Z-score is larger than or equal to 2.963 and 1.969 (the corresponding p-values are ≤ 0.003 and 0.049), respectively. We will reject the alternative hypothesis at the interim and final analyses when the absolute value of the Z-score is less than or equal to 0.338 and 1.969 (the corresponding p-values are ≥ 0.736 and 0.049), respectively. The secondary objective is to compare the post-operative pain in the first 24

hours after surgery between the two treatment arms. The patients will be blinded for the treatment assignment to avoid potential biases.

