1.0 Objectives

1.1 Primary Objective

To determine whether the use of a caudal nerve block (CNB) in combination with general anesthesia (GA) in patients undergoing penile prosthesis surgery results in decreased post-operative pain medication usage compared with patients having GA-only.

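### Is a symmetric interim futility rule on |Z| wrong for a trial whose objective is a decrease in pain medication usage?

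*Combined protocol and SAP*

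**What the plan says.** The objective is directional. Section 1.1 asks whether adding the block "results in decreased post-operative pain medication usage compared with patients having GA-only", and section 11.2 repeats the aim for the PACU stay: to "determine if the CNB + GA can result in decreased post-operative pain medication usage during PACU stay comparing to the GA-only".

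The test is not directional. Section 11.2 sets a two-sided Type I error of 0.05 and one interim look at 52 of 104 patients with O'Brien-Fleming boundaries. The null hypothesis is rejected at the interim when the "absolute value of the Z-score is larger than or equal to 2.963", and at the final analysis at 1.969. For futility the plan will "reject the alternative hypothesis at the interim and final analyses when the absolute value of the Z-score is less than or equal to 0.338" (interim) or 1.969 (final).

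The reasons given for stopping early are "evidence that the CNB + GA treatment is superior to the GA-only treatment or there is no difference between the two treatment arms". Section 9.0 adds, without naming a direction: "Response to CNB will be assessed by differences in post-operative pain score, number of analgesic medications taken and time to discharge".

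**The concern.** Take positive Z as favoring CNB + GA. The trial then stops at Z = +0.338 but continues anywhere between -2.963 and -0.338, where a final significant benefit is less likely. For a directional aim this ordering looks backwards. Under no true effect, about 37% of trials would enroll the second 52 patients, half of them to an invasive block, after an unfavorable interim.

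Two wording points add to the impression. The reasons for stopping omit the case in which the block does worse, although Z <= -2.963 rejects the null. And stopping because there is no difference seems to claim more than 52 patients can show, since no equivalence margin is set. If these were real faults, patients could be exposed to no purpose and a futility stop could be over-interpreted.

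**Working it through.** **Inputs, all from section 11.2:** means 21.6 and 13.9 mg, so a difference of 7.7 mg; common SD 13.6; 52 per arm; interim at 52 patients (26 per arm assumed); boundaries 2.963 and 1.969 for rejection, 0.338 for interim futility. The half-effect of 3.85 mg used below is an assumption for illustration.

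**1. The plan's own figures.**
- Interim SE = 13.6 × √(2/26) = 3.772 mg; final SE = 13.6 × √(2/52) = 2.667 mg.
- Mean of Z under the planned effect: 7.7/3.772 = 2.041 at the interim, 7.7/2.667 = 2.887 at the end.
- Integrating over the interim and final Z with these boundaries gives power 0.8125 when the futility rule is followed and 0.8216 without it. Stated: at least 81%.
- Two-sided error is 0.0500 if futility is ignored (2 × 0.02498) and 0.0483 if it is always followed. Without futility stopping, the final critical value that gives 0.05 solves to 1.969, as stated.
- Two-sided p-values for 2.963, 1.969 and 0.338 are 0.0030, 0.0490 and 0.735 (stated 0.003, 0.049 and 0.736; the last is rounding).

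**2. Is the action defined for every interim Z?** Yes, from the |Z| rules alone:
- Z >= 2.963: stop, null rejected, lower usage with the block.
- 0.338 < Z < 2.963: continue.
- -0.338 <= Z <= 0.338: stop for futility.
- -2.963 < Z < -0.338: continue.
- Z <= -2.963: stop, null rejected, higher usage with the block.

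**3. The ordering that looks odd.** The chance of a final significant benefit, given interim Z and the planned effect, is Φ(2.041 - (1.969√2 - Z)). This gives 34% at +0.338, 14% at -0.338, 4.1% at -1 and 0.3% at -2. The ordering is real. It follows from a two-sided test: the inner region ends trials unlikely to show a difference in either direction.

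**4. How often the unfavorable zone (-2.963 < Z < -0.338) matters.**
- No effect: reached in 36.6% of trials. Of these, 0.02% end with significant benefit. With no true effect such a result would be a false positive, so a tiny figure is what the design should deliver.
- Half the planned effect (3.85 mg): 8.7%.
- Planned effect: 0.9%, and 8.7% of those still end with significant benefit.
- Block worse by 7.7 mg: 78%. Of these, 81% end with significantly higher usage, so continuing is informative.

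**5. The alternative: stop for futility if -2.963 < Z <= 0.338, other boundaries kept.**

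| | Symmetric (plan) | Directional |
|---|---|---|
| Power at 7.7 mg | 81.25% | 81.17% |
| Expected size, no effect | 90.1 | 71.0 |
| Expected size, 7.7 mg | 92.9 | 92.4 |
| Futility stop at 3.85 mg | 16% | 25% |
| Lower-tail error, no effect | 0.0241 | 0.0016 |
| Total two-sided error | 0.048 | 0.026 |
| Power to show block 7.7 mg worse | 81% | 18% |

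The directional rule also still stops at Z = +0.338, the point where the 34% chance of success is given up.

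**6. The no-difference wording.** The futility region corresponds to an observed difference within 0.338 × 3.772 = 1.27 mg. The unadjusted 95% interval is the estimate ± 1.96 × 3.772 = ± 7.39 mg, so its upper limit runs from 6.12 to 8.67 mg across the region. It excludes 7.7 mg when Z < 2.041 - 1.96 = 0.081, which is (0.081 + 0.338)/0.676 = 62% of the region. If the true benefit is 7.7 mg, the region is hit in 3.6% of trials. A futility stop is thus evidence against the planned effect, but not proof of equivalence. The plan's decision rule claims only the former: it rejects the alternative hypothesis.

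**The case for a change.** The best case for the concern is that the remedies are cheap. If the investigators have no interest in showing that the block raises usage, a directional futility rule saves about 19 patients on average under no effect (90.1 - 71.0) for less than 0.1 percentage point of power at the planned effect, and it cannot inflate the two-sided error. The text also never says how a result favoring GA-only would be read, and an interim interval that still admits a benefit of 6.1 mg sits badly with talk of no difference.

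The arithmetic stands. What it shows is an efficiency trade-off, not a fault. The saving is bought by giving up most of the ability to show that an invasive add-on increases usage, in a setting where section 2.2 reports no publications for this surgery. Reasonable statisticians would differ on that exchange, and the plan's side of it agrees with its stated two-sided 0.05 level.

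The reading of Z <= -2.963 needs no separate rule, because rejecting a two-sided null with higher usage under the block means higher usage. Softer wording and a confidence interval after a futility stop would be good reporting, but no section commits the trial to a claim of equivalence.

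**Conclusion.** The concern does not hold. A directional objective tested two-sided is ordinary practice, a symmetric inner futility region is a recognized companion to such a test, and it implements the second of the plan's two stated reasons to stop. Power (81.25%), two-sided error (at most 0.050) and boundaries all reproduce, and each interim value leads to a defined action. Under the planned effect the disputed zone is reached in 0.9% of trials. What is left is a matter of wording in the reasons for stopping, which touches no decision or test result.

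This rests on 26 patients per arm at the interim, SD 13.6 treated as known, a normal approximation, and no allowance for dropout, since the plan states none.

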5.0 Treatment Plan

5.1 Preoperative

- 5.1.1 After consents for surgery and study participation are signed, patients will be registered for the trial by the research staff. Patients will be randomized (1:1) using a computerized randomization scheme.
- 5.1.2 Patients will be randomized (1:1) to one of two groups:
 - Group I, Treatment Group: Patients receive a caudal nerve block prior to surgery and receive general anesthesia during surgery.
 - Group II, Control Group: Patients receive general anesthesia during surgery without a caudal nerve block.
- 5.1.3 Patients in both groups will receive Famotidine 20mg IV, up to 1-2mg IV Midazolam and 25-50mcg IV Fentanyl in the holding area prior to the start of surgery.
- 5.1.4 Patients who are age 70 and older will not receive Midazolam 2mg IV in the holding area prior to the start of surgery.
- 5.1.5 Patients in Group II will receive Fentanyl 50-250mcg IV in the holding area prior to the start of surgery.

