5.2 Intraoperative

- 5.2.1 Group I Treatment Group
 - If the patient is randomized to Group I, the patient will receive general anesthesia using Propofol titrated for induction. The airway will be secured thereafter. The caudal block will be performed as a bolus injection into the caudal canal in the OR by the attending anesthesiologist using 1% Ropivacaine (max 5mg/kg) + 1:400,000 Epinephrine + Decadron 10mg + Clonidine 100mcg. Patients will be continuously monitored by ASA quidelines.
 - Anesthesia will be maintained with Sevoflurane 1.3-2.5% or Desflurane 2.5-8.5%, oxygen, air, nitrous oxide and Fentanyl as needed. At the completion of surgery, reversal of muscle relaxant with Glycopyrrolate 0.2mg IV for each 1mg IV of Neostigmine (max 5mg) will be given as indicated.

[figure not shown]

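### The trial is called blinded, but blinding is stated for patients only; nothing masks the PACU providers whose scoring and dosing produce the primary endpoint, or the follow-up callers

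*Combined protocol and SAP*

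**What the plan says.** Section 11.2 opens with "This is a randomized, blinded trial" and ends with "The patients will be blinded for the treatment assignment to avoid potential biases". It names no other group as blinded.

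Section 11.1 defines the outcome: "The primary endpoint is the post-operative pain medication usage during PACU stay". Section 5.3 describes how that outcome arises. On the pain score, 5.3.2 says "When using the NRS for pain, the provider will ask", and the patient answers with a number from 0 to 10. On treatment, 5.3.3 says "Pain will be treated and documented in the PACU dependent on the patient's pain score". Fentanyl steps begin at scores 3, 6 and 9, with reassessment at 15±5 minutes. Under 5.3.4, use above 250 mcg of fentanyl leads to a change to Dilaudid.

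The arms differ by a visible procedure. In Group I, section 5.2.1 says "The caudal block will be performed as a bolus injection into the caudal canal in the OR by the attending anesthesiologist". For Group II, section 5.1.2 says "Patients receive general anesthesia during surgery without a caudal nerve block". No sham, matched dressing or concealment of the anesthesia record is described.

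Later data come from a next-morning assessment, by telephone if the patient has gone home (5.3.6, 5.3.10), and from a day-3 call (5.3.9 and section 7.0). Nothing is said about what the callers know.

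**The concern.** Blinding the patient protects the patient's answer. It does not protect the steps that turn the answer into the endpoint: asking, recording, timing the next assessment and giving the drug. Those steps belong to PACU providers, and the plan does not mask them.

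A provider who knows that a block was placed, and expects it to work, could handle a borderline score differently. If that lowered recorded use in the CNB arm, the primary comparison would shift toward the block without any real analgesic effect. Readers would also take the word blinded to cover the people who generate the outcome, which the text does not support. The callers are a lesser matter, because their data lie outside the primary endpoint, but the same gap exists for the 24-hour and day-3 outcomes.

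**Working it through.** **Who is masked, role by role**

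| Role | Part in the outcome | Blinding stated? |
|---|---|---|
| Patient | Gives the NRS number | Yes (11.2) |
| Attending anesthesiologist | Performs the block (5.2.1), so knows the arm | No, and not possible |
| PACU provider | Asks for and records the NRS, gives and documents the opioid (5.3) | Not stated |
| Next-morning and day-3 callers | Collect pain and medication data (5.3, 7.0) | Not stated |

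**Where discretion remains in the PACU**

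1. At the cut-offs of 3, 6 and 9, a one-point difference in the recorded score changes the fentanyl dose by 25 mcg (0 to 25, 25 to 50, 50 to 75).
2. Reassessment after a dose may fall anywhere from 10 to 20 minutes (15±5).
3. After the change to Dilaudid, 5.3.4 gives an amount per dose and a total but no score bands. The heaviest users are therefore dosed without the fixed steps.

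**The plan's own figure**

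Inputs from 11.2: 52 patients per arm; means 21.6 and 13.9 mg, so a difference of 7.7 mg; common SD 13.6 mg; interim at 52 of 104 patients; rejection at |Z| ≥ 2.963 and 1.969; interim futility at |Z| ≤ 0.338.

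- Standard error of the difference: 13.6 × √(2/52) = 2.667 mg.
- Drift of the final Z: 7.7 / 2.667 = 2.887. Drift at the interim: 2.887 × √0.5 = 2.041.
- Probability of crossing the upper bound at either look, with futility binding, by numerical integration over the interim Z: 81.2%. This agrees with the stated power of at least 81%.
- With zero drift, the two-sided error is 4.83%, so the chance of a false claim in favour of CNB is 4.83% / 2 = 2.4%.

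**Illustration of bias**

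Suppose there is no true effect, but recorded use in the CNB arm is lower by b mg on average. The drift becomes b / 2.667, and the same integration gives:

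| b (mg, assumed) | Drift of final Z | Chance of a false claim for CNB |
|---|---|---|
| 0 | 0 | 2.4% |
| 0.5 | 0.187 | 3.7% |
| 1 | 0.375 | 5.5% |
| 2 | 0.750 | 10.9% |

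For scale, the documents give no fentanyl-to-morphine conversion. If 100 mcg of fentanyl is assumed to equal 10 mg of IV morphine, one 25 mcg step is 2.5 mg. Then b = 0.5, 1 and 2 mg correspond to a net loss of one step in 20%, 40% and 80% of CNB patients (0.5/2.5, 1/2.5, 2/2.5).

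**The case against.** The strongest reply is that the design already protects the endpoint well. The blinded patient supplies the number in answer to a scripted question. Section 5.3.3 fixes the fentanyl amount for each band. A score recorded low once is followed by another assessment, so persistent pain would prompt a further dose and part of any shortfall would be made up. Both arms share the same PACU discharge criteria (5.3.5). Section 11.2 also says in plain terms who is blinded. All of this stands, and it is why the bias, if any, may be small. It does not close the three points of discretion listed above.

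A reader might infer more than the documents support:

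- **That PACU staff know the arm.** The documents are silent. Disclosure at handover is plausible, but no section describes it, and the callers' knowledge is equally unstated.
- **That staff score the pain.** They elicit and record it; the patient provides it.
- **That the error rates above estimate the actual bias.** Neither the size nor the direction of any bias can be drawn from the documents. The rates are arithmetic on assumed shifts.

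**Conclusion.** The concern holds as a gap in the design and an overbroad label. Blinding is stated for patients only, while the primary endpoint passes through PACU providers for whom no masking is planned; the callers are likewise unaddressed. The existing safeguards limit the possible bias but leave an avoidable route for it.

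The magnitude is unknown. Under the stated boundaries, an SD of 13.6 mg, 52 per arm and binding futility, even a 1 mg average shift would more than double the one-sided error, from 2.4% to 5.5%. That conclusion depends wholly on the assumed shift. The planned sample size and power are not in question. The change should be made, but the documents do not show that the trial's result would be biased.

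**What to change.** In 11.2 and 5.3:

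1. State that the people who elicit and record the NRS in the PACU, and the telephone callers, are not told the study allocation as far as safe care allows.
2. Use the same sacral dressing in both arms.
3. Record any assessor who learns the arm, so that the extent of unblinding can be reported.
4. If masking in the PACU is not feasible, describe the trial as patient-blinded only, in the protocol and in reports.

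How clinical information about the block is communicated for safety should be left to the investigators; this point proposes no rule on it.

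The cost is a dressing, wording in two sections and a short unblinding record, plus any local arrangement needed to keep assessors unaware. Sample size, power and analysis do not change. The limitation is that some unblinding will still occur, which is the reason for recording it.
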